### **Outcome Measures of Functional Performance (Aim2, Hypothesis 1):**

Measures of motor function, PD QOL and explanatory measures of executive function, procedural learning, and spatial cognition will be conducted at evaluations (pre, post and 1 month follow-up). All evaluations will be performed in the safety-monitored Movement Analysis Laboratory at the Atlanta VAMC. All outcome measures will be directly measured with an instrument or self completed by the participant, except for BBS and other scales judged by a trained rater, which will be videotaped for a blinded and qualified rater (e.g., trained physical therapy students or research assistants) not involved with the project otherwise.

#### **Primary measure of motor function: The Berg Balance scale (BBS) **

#### **Secondary measures of motor function**

- **Fullerton Advanced Balance test**
- **6 minute walk test**
- **Single and Dual Timed Up and Go test **
- **Limits of Stability test**
- **Gait-** assessed with a 6 m computerized GAITRite walkway (CIR Systems, Inc. Havertown, PA, USA).

#### **Explanatory variables**

##### **Participant QOL and satisfaction with program**

- **PD Questionnaire-39 (PDQ-39)Exit Questionnaire** – (administered only at post-test within one week of completion of training). 

#### **Executive function, procedural learning, and spatial cognition**

We will investigate aspects of executive function, procedural learning, and spatial working memory to characterize more effectively the therapy's impact. The following cognitive measures are explanatory evaluative instruments: **Executive function:** Three standardized tests of executive function will be used:

- **Wisconsin card sorting test (64 cards)** (Kongs et al., Western Psychological Services)
- **Color Word Interference Test** (Delis-Kaplan Executive Functions System)
- **Tower of London-** from Cambridge Neuropsychological Test Automated Battery-Tower Of London, because of impairments in individuals with PD. 

**Procedural learning:** Procedural learning will be used as a predictor for those who will benefit more from EG training, which makes use of automatic processes already learned. Procedural learning ability will be measured with the **Serial Reaction Time Task**, . Procedural learning becomes more impaired with disease progression. 

**Spatial Cognition:** Remembering spatial patterns and relationships to others is essential in dancing, and true of both IG and EG training. The **Body Position Spatial Task** and **Corsi Blocks** test (previously described) will be also used as tests of spatial ability.

If we note improved cognition in conjunction with mobility improvement in both IG and EG groups, future studies will investigate neural areas related to the particular construct with fMRI. If we note cognitive improvements in one type of training, but not another, we will have additional information related to mechanisms by which particular forms of training are effective.

### **Procedures and Outcome Variables of Aim 2, Hypotheses 2 and 3:**

The same fMRI data acquisition, activation paradigm and preprocessing procedures, outlined in Aim 1, will be used for participants in each of the IG, EG and BC groups to determine BOLD activation (Hypothesis 2) while performing IG and EG tasks. We will also perform RSfcMRI data acquisition and preprocessing (Hypothesis 3), detailed here:

**Resting state functional connectivity MRI procedures:** At each scanning session, we will collect approximately 9 minutes of fMRI data from participants as they rest quietly in the scanner. Participants will be provided foam padding and towels to restrain head motion, while they look at a gray screen. They will be instructed to keep their eyes open, not to think of anything in particular, nor to fall asleep. Examiners will monitor the participants' eyes in a mirror and prevent them from falling asleep. We plan to compare changes in RSfc of the STC and the CTC pathways before and after IG and EG partnered training. The particular regions examined will be determined through analyses conducted on imaging data collected in Aim 1. We will also investigate whether these changes in functional connectivity correlate with improvement on the UPDRS and on IG and EG foot-tapping.

**Resting State Functional Connectivity Image Data Preprocessing for Aim 2, Hypothesis 3:** RSfc data will be preprocessed to correct for head movements, linear drift, and physiological noise (pulse, respiration) and will be normalized to standard space. It is likely the first 8-10 scans will be discarded to account for saturation effects and for adaptation of participants to a novel situation. The RETROICOR algorithm will remove physiological noise arising from main frequency peaks of cardiac and respiratory fluctuations. Cardiac and respiratory function will be monitored with a photoplethysmograph on the left index finger and a respiratory belt around the abdomen. BOLD signal changes arising from low frequency fluctuations of cardiac and respiratory waveforms will be detrended using established methods. The physiological noise corrected data will be low-pass filtered (cutoff frequency: 0.1 Hz) to further isolate low frequency resting state BOLD fluctuations.

### **Potential Pitfalls/Alternative Approaches**

1. If no differences are noted between IG training and EG training on outcome measures, but results match those of the original therapy, we will know that leading and following alone are likely as effective as the original dual, (interdigitated) IG/EG training for improving mobility. To inform motor rehabilitation, we will then suggest patients and providers have a choice of training type: follow cues, or plan and self-initiate movement. As we are not directly observing a dual IG-EG form of training in comparison to EG and IG, observed in isolation, we cannot determine whether EG or IG is better than dual IG-EG. Switching between leading and following in dual training demanded 'set-switching', impaired in individuals with PD. Future Merit proposals will examine the effects of set-switching on neural pathways, and conduct a definitive comparison of IG, EG and dual IG/EG training, by building on data gained from this project. An alternative approach is investigating sequential forms of treatment, i.e., IG then EG training, and comparing the cumulative effects to training in isolation. If, as predicted by our

hypotheses, connectivity patterns do reflect training effects, with connectivity increases primarily in the STC circuit following IG training and in the CTC circuit after EG training, then both circuits may need to be upregulated therapeutically. Future studies will determine optimal doses of each to make evidence-based guidelines for therapy.

2. While hand movement neural activity is relatively well studied, far less is known about brain activity of foot movements. We are making assumptions about brain activity in foot movements based upon hand literature. Given that the foot and hand differ in localization of representation in the sensorimotor cortex, foot cortical control may differ fundamentally from that of the hand. Future work via the VA Merit system will more definitively characterize lower limb motor control, in conjunction with motor training for veterans with PD.
3. This project is novel in key domains: 1) the investigation of foot-tapping in IG and EG paradigms in PD is novel; 2) investigating IG and EG training effects on mobility and especially cognition is novel; 3) changes in neural activation in conjunction with training will be examined for the first time. Based on information we gather from this study, in the future we will conduct targeted studies to continue investigating cognitive differences and changes in neural activation between groups.
4. Future investigations will more definitively investigate what form of training, IG or EG, is best at a particular stage of disease, and for individual patients with particular symptomatology.

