### **Participant Randomization for Aim 2**

After screening and consent, participants will be randomized to one of three groups (IG, EG or the behavioral control (BC, Education)). Participants will not be blinded to treatment group, but the instructors of the interventions will be blinded to performance on all outcome measures, and raters of all functional performance measures will be blinded to treatment group. The PI will train raters, qualified research assistants, in proper administration of all measures.

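### A non-significant IG–EG comparison plus an undefined match to earlier studies is to be read as each role being about as effective as dual training

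*Combined protocol and SAP*

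**What the plan says.** Potential Pitfalls/Alternative Approaches, item 1, sets two conditions: "If no differences are noted between IG training and EG training on outcome measures, but results match those of the original therapy". If both hold, "we will know that leading and following alone are likely as effective as the original dual" training. An action follows: "we will then suggest patients and providers have a choice of training type".

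The same item concedes that dual training is not observed in this study, so "we cannot determine whether EG or IG is better than dual IG-EG". It leaves to later proposals the task to "conduct a definitive comparison of IG, EG and dual IG/EG training", and adds: "Future studies will determine optimal doses of each to make evidence-based guidelines for therapy". Item 4 of the section says: "Future investigations will more definitively investigate what form of training, IG or EG, is best at a particular stage of disease".

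Elsewhere in the plan:

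- Participant Randomization for Aim 2 lists three arms: IG, EG and health education.
- Significance frames the question as whether there is evidence that one of the two roles is superior.
- Statistical Analysis Plan for Aim 2 specifies a 3 × 3 repeated-measures ANOVA, with post hoc tests for within- and between-group differences on the BBS.
- Power Analyses for Aim 2, Hypothesis 1, gives a post hoc between-group sensitivity of d = 0.90 and an earlier BBS gain of 4 points.

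**The concern.** The sentence makes two inferences, and the design supports neither.

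1. **IG against EG.** Failure to find a difference is treated as evidence that the two roles are alike. The plan has no equivalence margin, no equivalence or non-inferiority test, and no rule based on a confidence interval. A non-significant result in groups of about 20 is compatible with gaps that may matter.
2. **Either role against dual training.** With no dual arm, this rests on a comparison with other studies. What counts as a match is not stated: no outcome, visit, medication state (testing is both ON and OFF) or tolerance is named. Only participants who complete all 20 lessons are analysed, which further complicates a comparison across studies. A larger sample would not remedy this gap.

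IG versus EG is a central comparison of Aim 2, and this is the passage that says how a null result will be read. At stake is a statement of similarity, passed on as a suggestion to patients and providers, that the data could not bear.

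**Working it through.** **Inputs from the documents** (Power Analyses for Aim 2, Hypothesis 1): 21 analysed per group; 25 recruited per group; 20% attrition; alpha 0.05 (two-sided assumed); d = 0.90; earlier gain of 4 BBS points with effect size above 0.8; minimal detectable change 2.84 points.

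**Assumptions:** pre–post correlation r of 0.5, 0.7 or 0.8. Gaps are in units of the SD of BBS scores at one visit. The documents give neither quantity.

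**Step 1. Reproduce the stated sensitivity.** Two-sample t test, noncentrality d·√(n/2). At d = 0.90, power is 0.812 with 21 per group and 0.792 with 20. The plan's figure reproduces. The rest uses 25 × (1 − 0.20) = 20 per group.

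**Step 2. Miss rates and interval widths.** For post-training scores alone, the chance of a non-significant result is 0.662 with a true 0.5 SD gap and 0.544 with a 0.6 SD gap. The 95% half-width is 2.024 × √(2/20) = 0.64 SD.

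Pre–post change scores are closer to the planned group × time analysis. Their SD is the single-visit SD times √(2(1 − r)), so the gap is divided by that factor before computing power, and the half-width is multiplied by it.

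| r | √(2(1 − r)) | Miss, 0.5 SD gap | Miss, 0.6 SD gap | 95% half-width |
|---|---|---|---|---|
| 0.5 | 1.000 | 66% | 54% | 0.64 SD |
| 0.7 | 0.775 | 49% | 33% | 0.50 SD |
| 0.8 | 0.632 | 32% | 17% | 0.40 SD |

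**Step 3. How much a null result says.** With no true gap, a non-significant result occurs 95% of the time. The ratio to its probability under a 0.5 SD gap is 0.95/0.662 = 1.4, 0.95/0.488 = 1.9 and 0.95/0.317 = 3.0 for r = 0.5, 0.7 and 0.8. That is weak to modest evidence for no gap over a half-SD gap.

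**Step 4. The same check in BBS points.** If the effect size is change divided by SD, 4/0.8 bounds the SD at 5. Taking the minimal detectable change of 2.84 points as the true gap (the plan does not set it as a margin), with 20 per group and change scores:

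| Assumed SD | r = 0.5 | r = 0.7 | r = 0.8 |
|---|---|---|---|
| 5 | 58% | 38% | 21% |
| 4 | 41% | 19% | 7% |
| 3 | 17% | 4% | 0.4% |

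The weakness is clear at SD 5 with low correlation and small at SD 3 with high correlation.

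**Step 5. The comparison with dual training.** No arithmetic applies. The arms section lists no dual arm, and the pitfalls item gives no tolerance around the 4-point benchmark, or any reference to it.

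**The case against.** The strongest reply is that this is discussion text. The Statistical Analyses section contains no equivalence claim, and no endpoint, test or sample size depends on the sentence. It says likely, sets two joint conditions, admits that dual training is not observed, and leaves the definitive comparison and guidelines to later work. If both roles reproduced the earlier gains, and the trial has a randomized control arm, offering either could be reasonable without formal equivalence. A benchmark of 4 points does exist in the power section.

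Much of this stands, and it is why the point is minor. It does not remove it. The caveat withdraws only a claim that one role is better than dual training; the missing arm equally rules out a claim of being as effective, and that claim remains. The suggestion to patients and providers follows from this trial's result, not from later work. Beating the control is not among the conditions, and the benchmark carries no tolerance.

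On the numbers, three criticisms are fair:

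- The 0.5 SD gap is illustrative, and at an SD below 5 it is under 2.5 points, less than the minimal detectable change.
- Results vary widely with the unstated SD and correlation.
- The miss rates are single-test upper bounds on how often the conclusion would be triggered, because the rule also requires no difference on the other outcome measures and a match.

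**Conclusion.** The concern holds, at minor severity. Followed as written, the plan would draw a conclusion of similarity that its design does not support. The lack of a dual arm and of a matching criterion does not depend on any assumption. The weakness of the IG–EG inference does: at 20 per group, a 0.5 SD gap is missed 66%, 49% or 32% of the time for r = 0.5, 0.7 or 0.8, with 95% half-widths of 0.64, 0.50 or 0.40 SD. The primary BBS analysis is unaffected; only the reading of a null IG–EG result changes.

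**What to change.** Replace the sentence in item 1 with wording such as:

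> *The IG–EG difference in BBS will be reported with its 95% confidence interval. A non-significant difference will be reported as inconclusive about similarity, unless the interval lies within a margin fixed in advance. Any comparison with earlier dual-training studies is descriptive and non-randomized.*

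Delete the statement that each role is as effective as dual training, and do not base the choice-of-training suggestion on a non-significant test alone. If similarity is to be claimed on other outcome measures, the same rule should apply to them.

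The cost is wording only if no margin is set. Using the margin exception means choosing and justifying a margin beforehand. The conclusion after a null result becomes weaker, and a tight margin will often be out of reach. For an illustrative ±0.5 SD margin, no true gap, 20 per group and change scores, simulation puts the 95% interval inside the margin about 0.2%, 8.5% or 37% of the time at r = 0.5, 0.7 or 0.8. With a 90% interval (two one-sided 5% tests) the figures are 3%, 28% and 58%, so reachability depends on the correlation and on the rule chosen.

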## **Risk to Subjects**

Sources of Materials: For blinded ratings and patient confidentiality, all measurement data will be coded. Patient records will be stored in a locked cabinet in a locked office and will be accessible only to the PI. Computer-based records will be maintained on a secure network with password protection. Collection, analyses and use of these data will be exclusively for research purposes.

## Potential Risks:

**Risk of breach of confidentiality:** One risk of participating in this study is the chance of a breach of confidentiality. **Protection against risk of breach of confidentiality:** The study team will try its best to prevent this by coding all measurement data. Patient records will be stored in a locked cabinet in a locked office and will be accessible only to the Principal Investigator at the Atlanta VA Medical Center. Computer-based records will be maintained on a secure network with password protection at the Atlanta VA Medical Center. Collection, analyses and use of these data will be exclusively for research purposes. Videotapes of each trial will be available only to study personnel and kept in a file cabinet in a secure office at the Atlanta VA Medical Center. Permission to share video images and/or use these images as part of professional/scientific presentations will be obtained during the informed consent process.

## **Protection against risk of breach of confidentiality with fMRI data:**

**Neuroimaging Core Facilities:** The Emory Neurology Department (in coordination with the VAMC) has dedicated approximately 700 sq ft of space for a functional neuroimaging laboratory called the Brain Imaging, Rehabilitation and Cognition (BIRC) Laboratory under the direction of [name] (mentor/co-investigator). For data housing and analysis, the lab contains a high capacity (20 IRB 60613 Motor Training in PD

Study Version 6/14/16

terabyte) storage system as well as 5 multi-processor Linux data analysis workstations, all of which reside on a private gigabit ethernet network within the Emory domain. Only *approved VA personnel* are allowed to access this data, as it is administered and maintained by the VA Rehabilitation R&D Center of Excellence in Atlanta. Data security is maintained through need-only permissions and access control, while secure, encrypted backups maintain integrity and longevity of datasets. Importantly, all data will be *non-identified and scrubbed of all 18 HIPAA identifiers*. All servers are housed in secure server rooms, monitored 24x7 by electronic video and security personnel. [name] will offer mentorship on this project and will give [name], the PI, unfettered access to lab resources. While completing the proposed research study, [name] will complete fMRI analysis at the neuroimaging lab and have the benefit of the use of its testing rooms, technicians and data storage capabilities.

**Physical risks:** Physical activity interventions for PD-related motor impairments pose minimal risk of fatigue, and the possibility of delayed onset muscle soreness. However, previously we have not had complaints or reports of soreness resulting from physical activity associated with partnered dance programs for people with PD, for older frail adults with low vision, or for those with mental illness. The intervention to be employed, adapted tango, has previously been demonstrated to be effective at reducing fall risk as measured by a standardized balance scale, but all efforts will be made to ensure the safety of participants. Every participant will be frequently encouraged and reminded to take breaks *ad libitum* during testing and classes. Also, during all testing and classes, the PIs, the teacher trainees and trained assistants will continually monitor participants for: fatigue, instability and other reasons for discontinuing evaluations or training.

### **Plans to minimize adverse physical sequelae during the intervention:**

The following procedure, which was previously successful with other dance interventions for people with PD and oldest-old adults with low vision will be employed to minimize risk of falls and ensuing physical sequelae:

During classes participants will be continually monitored by the teacher trainee and trained assistants for fatigue and instability. The trained assistants will be instructed that their primary purpose is to prevent falls or other adverse events. Furthermore, to avoid accident outside of the class time, participants will be instructed not to practice the dance steps they learn at home or elsewhere outside of the class. Participants will be instructed to practice dance steps only when supervised by the instructor and assistants. Participants will be asked about their fall history at each observation, monthly during the intervention and all events will be documented.

### **Plans to minimize risks during Imaging:**

No one with deep brain stimulator implants will be allowed to participate in imaging.

The risks associated with the imaging procedure are the same as those associated with conventional MRI. Specifically, movement or heating of metallic implants is a potential risk, and so subjects will be extensively screened to exclude people with metallic implants, fragments, or pacemakers. Some individuals experience claustrophobic reactions in the scanner. Subjects will be informed of this prior to the study, but because it is difficult to predict who will have such a reaction, this is not a specific exclusion criterion. During the scans themselves, any subject experiencing claustrophobia will be removed from the scanner immediately. There is no invasive component to this study; therefore, discomfort, bruising, and/or infection are not risks.

There may be additional risks associated with scanning at 3T, which we address:

Effect of the static field: The FDA has approved for routine clinical use, scanners up to 4.0 T. The system that we will be using is FDA approved. There is no conclusive evidence for irreversible or hazardous bioeffects to acute, short-term exposures of humans up to 2.0 T (Shellock and Kanal, 1996). Studies have indicated some side-effects at 4.0 T, namely unusual sensations including nausea, vertigo, and metallic taste (Schenck, 1991). However, there is no evidence that this is either irreversible or harmful. If subjects experience unusual sensations, they will be withdrawn.

Effect of the gradient field: MRI operates by rapidly changing small additional fields, called gradients. By Faraday's induction law, a changing magnetic field will induce electrical currents in any conductor. Thus, rapid cycling of the gradient field can induce peripheral nerve stimulation. However, this is not substantially different at higher magnetic fields since the gradients are separate from the main magnet. Should participants experience peripheral nerve stimulation (e.g., tingling or twitching), the principal investigator and staff will withdraw the participant from the study.

Effect of the RF electromagnetic field: The fundamental principle of MRI is that protons are excited by sending in an RF pulse at their resonant frequency for the magnetic field. The FDA provides guidelines for the safe use of MR systems, which includes specific recommendations for how much RF power is safe. They use the "specific absorption rate," or SAR. The SAR is the mass normalized rate at which RF power is coupled to biologic tissue and is typically indicated in units of watts per kilogram (W/kg) (NRCP, 1986). The FDA provides recommendations for two alternative safe levels of exposure to RF energy during MR procedures, primarily to control the risk of systematic thermal overload (heating) and local thermal injury. These are (FDA, 1988):

(a) The exposure to RF energy below the level of concern is an SAR of 0.4 W/kg or less averaged over the body, and 8.0 W/kg or less spatial peak in any 1 g of tissue, and 3.2 W/kg or less average over the head;

OR

(b) The exposure to RF energy that is sufficient to produce a core temperature increase of 1 deg C and localized heating to no greater extent than 38 deg C in the head, 39 deg C in the trunk, and 40 deg C in the extremities, except for patients with impaired systemic blood flow and/or perspiration.

We will adhere to the recommendations for the head, which is also monitored by Siemens' built-in monitor.

